**Reviewer 3 (optional)**

Date

1    **Scientific Assessment: Method 3**

2    **Study Title:** *Effects of anodal transcranial direct current stimulation (a-tDCS) on naming in*  
3    *patients with non-fluent aphasia.*

4    **PI:** *[name] CCC-SLP*

5    **Co-investigator:** *[name] CCC-SLP*

6       • **Is the rationale for the study clearly stated and is the rationale scientifically**  
7    **sound?**

8    The emerging evidence of the relationship between working memory (WM) and naming  
9    offers a unique opportunity to investigate the effects of upregulation of WM systems and the  
10   effect on naming in nonfluent aphasia. Transcranial direct current stimulation (tDCS) is a  
11   non-invasive neuromodulation tool that presents a low current that induces bi-directional  
12   polarity-dependent changes in the cortex to facilitate focal, prolonged shifts in cortical  
13   excitability at or around the time stimulation is provided . Anodal tDCS (a-tDCS), in which  
14   the positively charged electrode is placed over the targeted cortical region, has been shown  
15   to increase cortical excitability (upregulation), similar to long-term potentiation (LTP).  
16   Combining a-tDCS with behavioral-based approaches has been suggested to enhance the  
17   learning process and increase the likelihood of retention. Although there is no specific  
18   neurophysiologic evidence to identify suppression of dorsolateral prefrontal cortex (DLPFC)  
19   in participants with aphasia, it has been implicated in naming deficits due to its role in  
20   working memory. tDCS has been applied to the DLPFC to target working memory, to  
21   date, there have been no investigations using a-tDCS to the DLPFC to influence naming  
22   skills in non-fluent aphasia. The overarching goal of this study is to explore the relationship  
23   between WM and naming by investigating the effects of a-tDCS to left DLPFC on naming  
24   accuracy and naming reaction times (RTs) in non-fluent aphasia. The primary purpose of this  
25   study is to 1) establish feasibility and safety of applying a-tDCS to the left DLPFC in patients  
26   with Broca's aphasia combined with behavioral naming treatment.  
27

28       • **Are the aims and corresponding hypothesis clearly stated?**

29    **Aim 1:** *Determine feasibility and safety of applying a-tDCS to the left DLPFC in Broca's aphasia.*  

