30   Two conditions: 1)a-tDCS (2mA for 20 minutes) will be applied over the left DLPFC followed  
31   immediately by behavioral naming therapy and 2) sham tDCS followed immediately by  
32   behavioral naming therapy will be presented to participants with non-fluent aphasia. *Hypothesis*  
33   1: no adverse events will be reported during or following this treatment and all participants will  
34   complete the study.  
35

36   **Aim 2:** *Identify effectiveness of a-tDCS to the left DLPFC combined with behavioral naming*  
37   *treatment in Broca's aphasia and establish a sample size for future investigations of this nature.*  
38   A small sample size will be used in this study to investigate effectiveness of the use of a-tDCS  
39   to the left DLPFC with behavioral therapy to target naming in non-fluent aphasia. *Hypothesis 2:*  
40   Improvements in working memory, naming reaction time and naming accuracy will be observed  
41   after the real a-tDCS condition but not after the sham a-tDCS condition.  
42

1     • **Is the primary outcome (and secondary outcomes, as appropriate) clearly  
2     defined?**

3     Primary outcomes include: naming accuracy on treated and control items, naming RTs on  
4     treated and control items, performance on WM tasks, and motor speech tasks.

5     • **Are there adequate preliminary data in the literature (or from the investigator) to  
6     justify the proposed research? Has an adequate literature review been done to  
7     support this study?**

8  
9     WM systems are short-term, temporary stores that are activated when active manipulation of  
10    items is necessary. It could be argued that all linguistic tasks invoke WM systems since the  
11    execution of any linguistic task requires the ability to maintain activation of a representation until  
12    the targeted linguistic process is complete. Indeed, the close relationship between language  
13    and WM is represented in many WM models. Over the past few decades, there has been  
14    increasing recognition that aphasia is frequently accompanied by deficits in WM systems.  
15    Furthermore, such deficits adversely impact linguistic performance in aphasia. Accordingly,  
16    treatment protocols are being developed on the premise that treatments aimed at improving WM  
17    systems will improve linguistic function in aphasia. While a variety of WM treatment  

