27 effects remain after the SHAM condition. If performance on naming RTs is +/- 1 standard  
28 deviation from the individual's benchmark mean, the REAL treatment condition will begin. If  
29 performance on naming RTs is > +/- 1 standard deviation from the individual's benchmark  
30 mean, REAL treatment will be postponed until the mean RTs fall within +/- 1 standard deviation  
31 of the benchmark. Periodic checks will be conducted weekly to identify when to begin REAL  
32 condition. Once there are minimal differences between naming RTs on the second word list,  
33 the REAL treatment will be initiated.

34

[figure not shown]
35 *Outcome measures:*

36 Two different word lists will be generated; a different list will be used for each treatment  
37 condition to control for exposure and learning effect. Pretreatment testing outcome measures will  
38 be recorded for 5 consecutive days for each outcome measure including: 1) naming accuracy 2)  
39 naming RTs on both word lists 3) performance on motor speech tasks and 4) performance on  
40 working memory tasks. Stability of baseline performance, defined as no more than 20%  
41 difference between scores, will be obtained in five consecutive sessions. In addition, outcome  
42 measures will be obtained immediately after each treatment session. Five maintenance  
43 outcome measures will also be obtained upon completion of treatment. These sessions will take  
44 place at the Clinical Translational Science Institute (CTSI) on [name] on the University  
45 of MN campus. An adverse events questionnaire will also be given after each treatment session  
46 as a mechanism of participants reporting any discomfort.

47  
48  
49

50

1 **Figure 1. Treatment Schedule**

6 *tDCS Protocol.*

7 Treatment sessions will take place at the University of MN Clinical Translational Science  
8 Institute. Each participant will be seated comfortably in a chair. A swim cap will be placed on  
9 the participant's head to identify cranial landmarks for accurate electrode placement. The area  
10 referred to as F3 by the International 10/20 system for electroencephalogram electrode  
11 placement has been established as the optimal location for targeting the left DLPFC.  
12 The F3 region will be located by marking the vertex (the midpoint between left and right tragus  
13 and midpoint between nasion and inion), measuring the head circumference. When these  

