14 measurements are entered into the Beam F3 Locator Software, additional values are provided  
15 to reliably identify the location of F3. Once F3 has been established, two saline soaked surface  
16 sponge electrodes (35cm) will be prepared and placed. For optimal anodal stimulation to the  
17 DLPFC, the anode will be placed over F3 and the cathode will be placed over the right  
18 supraorbital region. A current of 2mA will be delivered for 20 minutes  by a multichannel  
19 transcranial current stimulator (Starstim, Neuroelectrics Corporation; Cambridge, MA). a-tDCS  
20 will be applied before and during behavioral treatment in the design specified below.

25 *Behavioral-Based Naming Treatment Protocol.*

27 *Stimuli.* Eighty black-and-white line drawings will be obtained from on-line clip art websites.  
28 Picture names will be normed using five to ten English-speaking volunteers who will be asked to  
29 provide the names of the pictures. Cues words will be paired with the pictures if the words  
30 represent an associative or thematic relationship. Therefore, the words will be chosen that  
31 represent a concrete attribute (e.g., the picture, SHARK, is paired with the cue word *teeth*),  
32 location (e.g., the picture, SHARK, is paired with the cue word *ocean*), and either function or  
33 category (e.g., the picture, SHARK, is paired with the cue word, *fish*). The selection criteria for  
34 choosing these particular attributes is based on a classification criteria of thematic relations .  
35 Moreover, there is empirical evidence that that associative relations would prove beneficial in a  
36 naming treatment paradigm . Commonly used phrases (e.g., *great white shark*) or compound  
37 words (e.g., *bluefin shark*), synonyms or antonyms will be excluded. These cue words will be  
38 obtained from a semantic features normative database , which provides not only semantic

1 features information but categorical information as well. Two lists of 20-items will be created,  
2 which will be presented to each participant in order to avoid presenting the same list across the  
3 conditions. Pictures used in both lists will be balanced in terms of visual complexity and  
4 familiarity ratings. Words used in all conditions will be balanced in terms of lexical frequency  

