5 and word length. Familiarity ratings will be obtained from a normative database. Visual  
6 complexity ratings will be also obtained from a group of 20 individuals using the instructions and  
7 rating scales as reported in Snodgrass and Vanderwart's article. The CELEX database, will  
8 be consulted to determine lexical frequency of the words (cues) used in the study. An additional  
9 40 pictures will be selected for a control (untreated) list that will be used only during baseline  
10 and post-treatment testing. Performance on treated and untreated lists will be compared to  
11 determine treatment effects and possible generalization effects.

12  
13 *Naming Treatment Procedures.* All participants will be provided the same protocol, which will  
14 highlight the process of rehearsing the cues associated with the picture name. Treatment  
15 sessions will last until each participant has gone through the treated items twice. To insure  
16 control during the protocol, a graduate student trained in the protocol will administer the  
17 treatment steps. She will be blinded to the objectives of the study and conditions that are being  
18 administered. Treatment sessions will be video recorded for reliability purposes. To insure that  
19 she is not aware of when tDCS is being administered, a screen will be in place between the  
20 tDCS machine and the treatment table. The protocol is provided in Table 1.

21  
22 **Table 1. Naming Treatment Protocol.**

Steps Involved in Naming Treatment Protocol	
Picture Presentation	Participant will be asked to name the picture. If she/he is unable to provide the name within 10 seconds, the name will be provided.
Cue Presentation	Cues that accompany the picture will be presented. He/she will be asked to read each cue word as it is presented. If he/she is unable to read the word spontaneously within 10 seconds, he/she will be asked to repeat each word after the clinician.
Cue Rehearsal	Both picture and cues are taken away. Participant is asked to rehearse the cue words silently for 10 seconds.
Cue Self-Generation	Participant will be asked to generate all three cues. For each instance that the participant is unable to provide a cue within 10 seconds, the cues will be provided. Once the cues have been provided, the participant will then be asked to provide the picture name.

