Picture + Cue Presentation	If the participant is unable to provide the name, the cues will be read, or if he/she is unable to read spontaneously, he/she will be asked to repeat after the clinician. If she/he is still unable to provide the picture name after the cue review, it will be provided.
Picture + Cue Review	Once the cues and picture are laid out on the table, the clinician will read each cue and name the picture. The participant will be encouraged to read/repeat with the clinician.

1  
2     • **Have the validity and reliability of measures been established or are there**  
3     **methods proposed for establishing validity and reliability?**

4  
5     Approximately 20% of each of the participant's behavioral treatment sessions will be  
6     observed by the co-investigator in order to obtain procedural integrity. Steps of the treatment  
7     protocol will be scored using a binary (+/-) coding system. Point-by-point agreement will be  
8     obtained. Reliability in scoring naming error types will also be obtained using a table that  
9     lists the most common aphasic naming errors, definitions and examples of each error type.  
10    Point-by-point agreement will be obtained.

11  
12     • **Is the proposed subject population appropriate?**

13     Participants will be recruited via emails sent to Twin Cities metro area hospital and  
14     aphasia/stroke support groups. Potential participants will then be screened for eligibility for  
15     the study.

16     **Screening.** Potential participants will be seen for 2-3 sessions to undergo comprehensive  
17     cognitive-linguistic assessment to determine eligibility for the study. This assessment will  
18     take place within the participant's home to provide a comfortable, natural environment for the  
19     potential participant. Behavioral assessment measures will include the Western Aphasia  
20     Battery (WAB) which will be used to obtain overall language function via the WAB Aphasia  
21     Quotient (WAB AQ), the Boston Naming Test (BNT) in order to obtain naming function,,  
22     Apraxia Battery for Adults (ABA-2) in order to determine apraxia of speech severity, and  
23     working memory tasks to determine subvocal rehearsal processes and phonological short-  
24     term store abilities.

25     These participants must meet the following inclusionary criteria:

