19 each patient will be recorded and presented. In addition, the number of participants who failed  
20 to complete the study will be recorded and factors recorded. To the extent possible, the  
21 participants will be asked to continue to participate in the assessments to allow a consideration  
22 of intent to treat analysis.

23  
24 *Aim 2.* Means and 95% confidence intervals will be plotted and used for comparison of naming  
25 RTs, working memory performance and motor speech performance across treatment conditions  
26 for each subject (Deng, et al. 2013). Naming accuracy performance will be analyzed using  $d'$   
27 statistics for lexical data to determine magnitude of treatment effect. The effect size will be  
28 interpreted using benchmarks proposed by Beeson and Robey (2006) for lexical retrieval  
29 treatments: small ES = 4.0, medium ES = 7.0, large ES = 10.1. Naming RT mean and  
30 confidence intervals will be analyzed for changes within and across treatment conditions using  
31 visual inspection.

32  
33       • **Are all the proposed tests or measurements requested necessary to answer the  
34 scientific question?**

35 Yes. The proposed measures will allow investigators to report the feasibility and safety of  
36 the use of a-tDCS. The measures will also allow investigators to identify individual treatment  
37 effects of a-tDCS to left DLPFC combined with behavioral naming therapy on naming in non-  
38 fluent aphasia and through visual inspection and graphical analysis, compare effects to sham  
39 treatment. Naming RT and accuracy are sensitive measures of the participant's retrieval and  
40 learning of treated items. Motor speech performance will allow us to track changes in motor  
41 planning and sequencing abilities, which can influence naming RT and naming accuracy.  
42 And, performance on working memory tasks will allow for investigation of the influence of  
43 WM on naming and to provide additional evidence that a-tDCS to the left DLPFC may  
44 influence WM in individual participants.

45  
46       • **Are the investigators well qualified to conduct this study?**

47  
48 **Key Personnel**

1                   **Name**

2                   [name] CCC-SLP

3                   **Affiliation**

4                   University Wisconsin River Falls

5                   **Role**

6                   PI

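### Treatment-phase naming probes all follow same-session modelling of the treated names, and the plan does not separate them from the maintenance probes when it computes d' and RT summaries

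*Combined protocol and SAP*

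**What the plan says.** The primary outcomes are naming accuracy and RT on "treated and control items, performance on WM tasks, and motor speech tasks". Under Outcome measures, pretreatment testing runs on five consecutive days. During treatment the outcome "measures will be obtained immediately after each treatment session", and five maintenance measures follow the end of treatment. The text gives no spacing for the maintenance measures and describes no probe before a treatment session.

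Under Naming Treatment Procedures, "sessions will last until each participant has gone through the treated items twice", and each condition has its own 20-item list. In Table 1 the first step asks for the picture name; if the participant is "unable to provide the name within 10 seconds, the name will be provided". The name is supplied again if the participant still fails after the cue review. The last step applies to every item: "Once the cues and picture are laid out on the table, the clinician will read each cue and name the picture", with the participant encouraged to join in. The same visit delivers 20 minutes of active or sham current.

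For Aim 2, the statistical section plots means and 95% intervals for RT, working memory and motor speech by condition. It analyses accuracy with d' against benchmarks of 4.0, 7.0 and 10.1. It does not say which phase's probes enter these quantities. The section on whether the measurements are necessary reads naming RT and accuracy as measures of both retrieval and learning of the treated items.

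**The concern.** The baseline and treatment-phase probes differ in more than the treatment received so far. A treatment-phase probe comes minutes after the participant has heard, and probably repeated, the answers; a baseline probe does not. Some of the rise from baseline may be repetition that fades by the next day.

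Three uses of the data are exposed.

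- Each condition's d' is judged against absolute benchmarks, so nothing cancels there.
- Hypothesis 2 predicts improvement after REAL but not after SHAM. Therapy followed at once by a probe can produce apparent improvement after SHAM.
- Aim 2 is also meant to supply a sample size for later studies, and an effect that mixes immediate and retained gain could mis-size them.

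A separate question is whether an immediate REAL advantage could reflect the participant's state just after stimulation. The probe timing cannot exclude that.

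**Working it through.** The documents state no SD, expected gain or power calculation, so there is no figure of the plan's own to reproduce.

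**Name exposures before each probe (Table 1).** The name is given at the final review of every pass, and at up to two earlier steps if the participant fails. That is 1 to 3 times per pass. Two passes give 2 × 1 = 2 to 2 × 3 = 6 exposures per item per session. Baseline testing includes no therapy, so the count there is 0.

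**Time from exposure to probe.** 20 items × 2 passes = 40 presentations per session. The 10-second silent rehearsal alone takes 40 × 10 s = 400 s, or 6.7 min. If every explicit limit is used (10 s for the picture, 3 × 10 s for cue reading, 10 s for rehearsal, 3 × 10 s for cue generation), the total is 40 × 80 s = 3,200 s, or 53.3 min. Untimed steps are extra. The probe therefore follows the last modelled name within minutes, and the current within roughly an hour.

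**Shift in d'.** Assume d' = (later-phase mean − baseline mean) / baseline SD; the documents cite sources for d' but do not write it out. Each item named only because of same-session effects then adds 1/SD.

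The stability rule offers a rough upper limit for the SD. If 20% means percentage points of 20 items, baseline scores may span 4 items. The largest sample SD over five probes comes from a 3/2 split at the extremes (for example 0, 0, 0, 4, 4 relative to the lowest score). The mean is 1.6, the sum of squares is 3 × 1.6² + 2 × 2.4² = 19.2, and the SD is √(19.2/4) = 2.19.

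| Baseline SD (items) | d' added per transient item | Transient items that alone reach 4.0 | Transient items equal to the 4.0-to-7.0 step |
|---|---|---|---|
| 0.5 | 2.0 | 2.0 | 1.5 |
| 1.0 | 1.0 | 4.0 | 3.0 |
| 1.5 | 0.67 | 6.0 | 4.5 |
| 2.19 | 0.46 | 8.8 | 6.6 |

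**Effect of the choice of probes (illustration).** Assume a retained gain of 4 items and 2 further items named only in the immediate probes. Pooling five immediate and five maintenance probes gives an average gain of 4 + 2/2 = 5.

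| SD | Maintenance only | Pooled 5 + 5 | Immediate only |
|---|---|---|---|
| 1.0 | 4/1 = 4.0 | 5/1 = 5.0 | 6/1 = 6.0 |
| 1.5 | 4/1.5 = 2.67 | 5/1.5 = 3.33 | 6/1.5 = 4.0 |

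At SD 1.5 the same data fall below the small benchmark or reach it, depending on a choice that the plan leaves open.

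**REAL against SHAM.** Both conditions use the same therapy, number of passes and probe timing, on lists to be balanced for complexity, familiarity, frequency and length. If the transient gain is t in both, it drops out: (G_REAL + t) − (G_SHAM + t) = G_REAL − G_SHAM. An added amount c that arises only with active current does not drop out, and immediate probes alone cannot separate c from a retained difference.

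**The case against.** The case on the other side is substantial, and much of it stands.

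- **Cancellation.** Repetition is common to both conditions. A reader might infer that the REAL-SHAM comparison is biased by it, but the design does not support that beyond imperfect cancellation.
- **Transience of stimulation.** A reader might take the rationale's phrase "excitability at or around the time stimulation is provided" as an admission that the effect passes quickly. The same sentence calls the shifts prolonged, and the text goes on to long-term potentiation and retention. A short-lived effect is a possibility the design cannot exclude, not something the protocol states.
- **The aim.** Aim 2 speaks of effectiveness and Hypothesis 2 of improvement after the condition; neither mentions learning. The literature section treats immediate and long-term effects as both relevant, so an immediate probe is not outside the aim.
- **Ceiling.** One might suspect that immediate probes press both conditions towards 20 of 20. The documents give no baseline accuracy or expected gain to support this, and participants have moderate to moderately severe aphasia.
- **Existing data.** The maintenance probes could separate the two effects. The first-pass naming attempt on days 2-5 also precedes that day's modelling and is video recorded. It is not a declared outcome, however, and it follows at least some stimulation.
- **Silence.** The plan does not say that it pools phases. The cited d' sources and the treatment schedule figure, neither available here, may bear on this.

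What remains is that the text does not commit the analysis to probes free of same-session exposure, and within-condition d' is read against absolute thresholds where cancellation offers no help.

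**Conclusion.** The concern holds for each condition's own effect size and for the reading of improvement after SHAM. It holds for REAL-SHAM only as an inability to tell a possible short-lived effect of active current from retained gain. It is worth correcting, but it does not undermine a four-participant study whose stated primary purpose is feasibility and safety.

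The exposure imbalance of 2-6 against 0 follows directly from Table 1. Its effect on scores is unknown. The range of about 0.46 to 2.0 in d' per transient item rests on the assumed formula, on assumed SDs from 0.5 to 2.19 items, and on reading the 20% rule as a 4-item range. A relative reading of that rule would allow a smaller range at scores below 20, and so a lower SD limit and a larger minimum shift. It would be too strong to say that a 4-item transient gain by itself earns the small label. That is so at SD 1 (4/1 = 4.0), but at SD 2.19 the result is 4/2.19 = 1.8.

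**What to change.** 1. Probe treated-item accuracy and RT at the start of each treatment visit, before stimulation and therapy. Visits 2-5 then each give a next-day measure of what the preceding sessions left behind; visit 1 adds a further pre-therapy value.
2. State in the analysis that d' and the REAL-SHAM naming comparison use the visit 2-5 pre-session probes and the five maintenance probes.
3. Give the days of the maintenance probes.
4. If a post-session naming probe is kept, report it separately as an immediate effect. Keeping it also preserves same-time pairing with the working-memory tasks, which the protocol wants in order to study their influence on naming. Working-memory and motor-speech testing can stay where they are.
5. Reconcile the passages on the timing of the current. The aims and Treatment Design have it followed by therapy, while the tDCS Protocol has it before and during therapy. The interval from current to probe depends on this.

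No extra visits or participants are needed. The costs are a change of protocol wording, a naming effect that will probably look smaller and, if both probes are kept, one short extra probe per visit. If the post-session probe is dropped, naming and working memory are no longer measured at the same point in the visit.

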46    relationship to emotional well-being and functional communication, treatment that  
47    improves naming deficits will positively influence quality of life in many of these individuals.  
48    The approach taken to remediate naming deficits in aphasia is to treat impaired WM systems

1 on the premise that certain cognitive processes underlie linguistic functions in aphasia. This  
2 approach represents a departure from most behavioral-based naming treatment approaches,  
3 but reflects a growing recognition that WM systems in individuals with aphasia impact  
4 linguistic performance . The addition of a-tDCS as a neuromodulation tool to increase  
5 cortical excitability (upregulate) the working memory center to target naming is a novel  
6 approach in aphasia. These findings, , will provide valuable information regarding the role  
7 WM plays in naming and the potential benefit of using neuromodulation to the DLPFC to  
8 influence naming in aphasia.

9

- 10 • **Is the design of the study appropriate for the questions that are posed?**

11

12 *Treatment Design:*

13 A single subject cross-over design with a 4 week wash out period will be used. Two treatment  
14 conditions will be presented. The sham (SHAM) condition will consist of presentation of sham  
15 tDCS for 20 minutes followed by behavioral naming treatment. The real treatment condition  
16 (REAL) will consist of 20 minutes of a-tDCS to the left DLPFC followed by behavioral naming  
17 treatment. The length of behavioral naming treatment will depend on how long each participant  
18 takes to go through the treatment stimuli twice. A SHAM-REAL sequence will be used across all  
19 participants. Although order effects may be introduced using the same sequence across  
20 participants, the small number of participants makes it difficult to interpret any data that comes  
21 from using a counterbalanced presentation of treatment.

22 Treatment will be provided over five consecutive days. A minimum of a one-month washout  
23 period will be provided between the two conditions (Figure 1). Prior to initiating the REAL  
24 treatment condition, the naming RTs obtained on the second word list during the pre-treatment  
25 testing period (prior to the initiation of the SHAM condition) will be compared to the naming RTs  
26 obtained after the washout period. RTs will be analyzed to ensure that no lasting treatment  

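### Adverse events are solicited only by a questionnaire after each treatment session, so delayed events, chiefly after each participant's last REAL session, depend on unsolicited reports

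*Combined protocol and SAP*

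**What the plan says.** Feasibility and safety are the stated primary purpose of the study. Hypothesis 1, under Aim 1, reads "1: no adverse events will be reported during or following this treatment and all participants will" and goes on to predict full completion. How long the period after treatment lasts is not defined.

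Outcome measures gives the collection method: "of MN campus. An adverse events questionnaire will also be given after each treatment session", described "as a mechanism of participants reporting any discomfort". No recall period is given. The same section sets out the other contacts. Naming, motor speech and working memory are tested on five consecutive days before treatment, after every treatment session, and again in maintenance: "outcome measures will also be obtained upon completion of treatment. These sessions will take". The adverse events questionnaire is attached only to the treatment sessions.

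Treatment Design fixes the timetable: "Treatment will be provided over five consecutive days. A minimum of a one-month washout" period separates the blocks, and the order is the same for everyone: "takes to go through the treatment stimuli twice. A SHAM-REAL sequence will be used across all" participants. RTs are tested again after the washout and, if REAL is postponed, "of the benchmark. Periodic checks will be conducted weekly to identify when to begin REAL". These checks are described for RTs only.

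The Aim 1 analysis, in the statistical considerations section, says that the number and type of adverse events per patient will be recorded and presented. It gives no time window and no further method of collection.

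**The concern.** The hypothesis covers a longer period than the data collection does. An event that starts after the participant has completed the day's questionnaire is asked about only if another questionnaire follows and refers back to that time. No treatment session follows the last REAL session, so the interval after the complete course of real stimulation has no planned solicitation, although maintenance sessions are already scheduled.

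Two features raise the stakes. First, the hypothesis is a zero-event claim in four people, so one missed event is enough to turn a refuted hypothesis into a supported one. Second, the fallback is spontaneous reporting, and eligibility requires moderate to moderately severe non-fluent aphasia with apraxia of speech. These participants are poorly placed to volunteer a symptom. The study is also meant to prepare a larger trial, so an under-collected safety result would be carried forward.

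**Working it through.** The plan states no sample size calculation, error rate or power for Aim 1, so there is no figure of its own to reproduce. The check is a count of scheduled contacts.

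**Inputs**
- Participants: 4 (recruitment stops at four).
- Conditions: 2, SHAM then REAL for all (Treatment Design).
- Sessions per condition: 5, on consecutive days (Treatment Design).
- Washout: at least about four weeks (Treatment Design).
- Maintenance measures: five. The text does not make clear whether this is five in total or five after each condition.

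**Planned questionnaires**
- Per participant: 2 × 5 = 10. In total: 4 × 10 = 40.
- After REAL sessions: 4 × 5 = 20.
- Described at baseline, post-washout RT checks or maintenance: 0.

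**What follows each session**
- REAL days 1 to 4: 4 × (5 − 1) = 16 of 20 sessions have another questionnaire at the next day's session. It picks up overnight events only if it asks about the time since the last visit, which is not stated.
- REAL day 5: 4 × 1 = 4 of 20 sessions (20%) have no later questionnaire.
- SHAM day 5: the next questionnaire is the one after the first REAL session, at least about four weeks later and after real stimulation has been given. Unless it separates the two periods, a symptom from the washout could be counted under REAL.

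**Effect of adding the questionnaire at contacts already planned**
- After the last REAL session: from 0 to 5 per participant, or 4 × 5 = 20 in total, if the five maintenance measures are separate visits after REAL.
- If five follow each condition: 10 per participant, or 40 in total, of which 20 come after REAL.
- If the five are shared between conditions, fewer fall after REAL.
- One baseline session and at least one RT check add 2 or more per participant. The total rises from 10 to at least 10 + 1 + 1 + 5 = 17, or 10 + 1 + 1 + 10 = 22.

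**How often there would be something to miss**
The documents give no rate of delayed events. Assume a per-participant probability p of at least one delayed event after the last REAL session, independent across participants. The chance that at least one of four has such an event is 1 − (1 − p)^4:

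| p (assumed) | at least one of 4 |
|---|---|
| 0.05 | 0.19 |
| 0.10 | 0.34 |
| 0.20 | 0.59 |
| 0.30 | 0.76 |

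This is the chance that an event exists, not that it goes unreported. It shows when complete capture could decide whether Hypothesis 1 is supported.

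**The case against.** The strongest reply is that the plan collects more than a quick reading suggests. A reader might infer any of the following, and the documents do not support them:

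- *That nothing is solicited after treatment.* Each session is 20 minutes of stimulation followed by naming therapy, and the questionnaire comes after the session. Every one of them, including that on the final REAL day, therefore covers some time after stimulation, and those on days 2 to 5 may reach back to the day before.
- *That the questionnaire is given at once.* That wording belongs to the outcome measures: "measures will be obtained immediately after each treatment session. Five maintenance". For the questionnaire the text says only that it comes after the session.
- *That no questionnaire falls after either block.* This is true of REAL only. Five come after the last SHAM day, during REAL.
- *That pre-existing symptoms cannot be recognised.* The five SHAM questionnaires give each participant a reference before any real stimulation. It is partial, because it is obtained under sham procedures and always comes first.
- *That other reports are excluded.* The Aim 1 analysis is not restricted to the questionnaire, and symptoms mentioned at maintenance sessions could be recorded.

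It can also be said that Aim 1 is descriptive, that the documents give no reason to expect delayed events, and that Figure 1 (the treatment schedule) and some pages were not available and may contain further safety contacts.

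All of this narrows the point without removing it. Unsolicited reporting is permitted, but it does not replace asking in this population. No recall period is stated, so next-day coverage is possible rather than planned. Nothing in the reply covers the interval after the last REAL session.

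**Conclusion.** The gap is real and limited. In the text available, no solicited collection is described beyond the post-session questionnaires, the recall period is unstated, and the period after treatment named in Hypothesis 1 is undefined. The main exposure is the interval after each participant's final REAL session (4 of 20 REAL sessions, one per participant). The second is the interval of about four weeks or more after the last SHAM session.

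Missed delayed events can only move the safety result toward no events. The amount cannot be estimated from the documents. The missing baseline questionnaire is a separate and smaller matter and acts the other way, since a symptom already present could be counted as new.

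The conclusion assumes that the unavailable figure and pages add no questionnaire at other visits. The gain of 5 contacts after REAL assumes five separate maintenance visits after that block. Closing the gap would still leave a small safety sample: even with complete collection, zero affected of four has a one-sided 95% upper limit of 1 − 0.05^(1/4) = 0.53. The change is worth making because it concerns the stated primary purpose, is cheap beforehand and is hard to repair afterwards.

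**What to change.** 1. Give the same questionnaire at one baseline session, at each post-washout RT check and at each maintenance session. The RT check before REAL starts then closes the SHAM follow-up before real stimulation begins.
2. Have it ask about the time since the last contact and record the day of onset, so that overnight symptoms are separated from those of the current session.
3. State in Aim 1 what period after treatment Hypothesis 1 covers, and whether the five maintenance measures follow each condition or REAL only.
4. Report events by condition as same-day or after-the-block, marking those already present at baseline. Give the length of follow-up for each block, since the two may differ.
5. If Figure 1 or another section already provides such contacts, refer to it in Outcome measures.

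The cost is a few minutes at visits already planned, with no new visits or participants. The downside is that more minor symptoms will be recorded, which makes a strict zero-event hypothesis harder to meet. The baseline record and the split by condition help the reader to interpret them.
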